9.3.3 Covariates

Logistic regression model was used to estimate propensity scores based on all covariates listed below:

- ✓ Age
- ✓ Gender
- ✓ Speciality of prescribers of OAC
- ✓ Time from AF diagnosis to initiation of OAC
- ✓ History of stroke or transient ischemic attack yes/no
- ✓ History of myocardial infarction yes/no
- ✓ History of coronary artery disease yes/no
- ✓ History of heart failure yes/no
- ✓ History of diabetes mellitus yes/no
- ✓ History of dyslipidemia yes/no
- ✓ History of arterial hypertension yes/no
- ✓ History of peripheral artery disease yes/no

- ✓ History of peptic ulcer disease yes/no
- ✓ History of dementia yes/no
- ✓ History of malignant lymphoma yes/no
- ✓ History of leukemia yes/no
- ✓ History of solid tumor cancer yes/no
- ✓ History of kidney impairment yes/no
- ✓ History of liver disease yes/no
- ✓ History of valvular disease yes/no
- ✓ History of bleeding (gastro-intestinal, etc.) yes/no
- ✓ History of hospitalization yes/no
- ✓ CHA₂DS₂-VASC
- ✓ HAS-BLED Score
- ✓ Year of Initiating Treatment
 - Index date falling within 12 months starting from 14th of March in 2011 and then from 1st of March of each respective year in 2012 to 2016, then to 30 June 2016.
- ✓ Concomitant medication (prescription claims within the baseline period)
 - yes/no for the following:
 - ◊ aspirin
 - ◊ ticlodipine
 - ◊ cilostazole
 - ◊ clopidogrel
 - ◊ angiotensin receptor blockers or angiotensin converting enzyme inhibitors
 - ◊ beta-blocker
 - ◊ amiodarone
 - ◊ procainamide
 - ◊ disopyramide
 - ◊ flecainamide
 - ◊ pilcicainide
 - ◊ procainamide
 - ◊ calcium-channel blocker
 - ◊ digoxin
 - ◊ diuretics
 - ◊ statins
 - ◊ proton-pump inhibitor
 - ◊ H₂ receptor antagonist

The disease, condition/disease for AF risk score calculation, AF risk score, and concomitant medication are defined as [Table 4](#), [Table 5](#), [Table 6](#), [Table 7](#), [Table 8](#).

Table 4

Definition of clinical history

| Disease | Definition | |
|-------------------------------------|---|---|
| | ICD10code | prescription |
| Stroke or transient ischemic attack | I60-I64, G45 | - |
| Myocardial infarction | I21-I23 | - |
| Coronary artery disease | I251 | - |
| Heart failure | I110, I130, I132, I420, I50 | Prescribed furosemide (defined by generic name) |
| Diabetes mellitus | E100, E101, E109, E110, E111, E119, E14 | Prescribed drugs used in diabetes (defined by ATC code as A10) |
| Dyslipidemia | E78 | - |

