| Arterial hypertension | I10-I15 | Prescribed 2 or more types of anti-hypertensive (defined in Table 2b) |
| Peripheral artery disease | I702-I709, I71, I739 | - |
| Peptic ulcer disease | K22, K25-K28 | - |
| Dementia | F00-F03, G30 | - |
| Malignant lymphoma | C81-C88 | - |
| Leukemia | C90-C96 | - |
| Solid tumor cancer | C00-C80, C97 | - |
| Kidney impairment | N28 | - |
| Liver disease | K70-K77 | - |
| Valvular disease | I059, I089, I358, I38, I48 | - |
| Bleeding (gastro-intestinal, etc.) | K25-K29, K922 | - |

Table 5 Definition of anti-hypertensive

| Class/type | ATC code |
|--|---|
| Calcium channel blockers (CCB) | C08A0 |
| Angiotensin receptor blockers (ARB) | C09C0 |
| Angiotensin converting enzyme inhibitors (ACE) | C09A0 |
| Diuretics | C03A1, C03A2, C03A3, C03A7, C03A9 |
| Thiazide diuretic | C03A3 (Thiazide, plane), C02D0 (Rauvolfia alkaloids) |
| Beta blocker | C07A0 |
| Alpha-adrenoreceptor antagonists | C02A2 |
| Potassium-sparing agents | C03A1 |
| Others | C02A1 (Antihypertensives), C02A3 (Antihypertensives for pulmonary arterial hypertension), C09X0 (Other agents acting on the renin-angiotensin system) |
| Combination agents | C09D1 (ARB and diuretics), C09D3 (ARB and CCB) |

Table 6

Definition of condition/disease for AF risk score calculation

| Condition/disease | Definition | |
|---|---|--|
| | ICD10code | prescription |
| Congestive heart failure or left ventricular dysfunction | I110, I130, I132, I420, I50 | Prescribed furosemide (defined by generic name) |
| Stroke (ischemic stroke, transient ischemic disease, or systemic embolism) | I63, I64, G45, I74 | |
| Vascular disease (myocardial infarction, peripheral arterial disease, or aortic plaque) | I21-I23, I702-I709, I71, I739, I700 | |
| Abnormal renal function | I12, I13, N00-N05, N07, N11, N14, N17-N19, Q61 | |
| Abnormal hepatic function | B150, B160, B162, B190, K704, K72, K766, I85 | |
| Stroke (ischemic stroke or transient ischemic attack) | I63, I64, G45 | |
| Bleeding | I60, I61, I62, D62, J942, H113, H356, H431, N02, N95, R04, R31, R58, K250, K260, K270, K280, K290, S063, S064, S065, S066 | Aspirin and clopidogrel: defined by general name |
| Drugs (aspirin, clopidogrel, or non-steroidal anti-inflammatory drugs) | | Non-steroidal anti-inflammatory drugs defined by ATC code (EPHMRA) as M01A |
| Alcohol intake | F10, G312, G621, G721, I426, K292, K70, K860, L278, O354, T51, Z714, Z721 | |

Table 7

AF risk score calculation

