| Risk score | Disease/condition | Points if present |
|--|---|-------------------|
| CHADS ₂ (9) | Congestive heart failure or left ventricular dysfunction | 1 |
| | Hypertension | 1 |
| | Age \geq 75 years | 1 |
| | Diabetes mellitus | 1 |
| | Stroke (ischemic stroke, transient ischemic disease, or systemic embolism) | 2 |
| CHA ₂ DS ₂ VASc (10) | Congestive heart failure or left ventricular dysfunction | 1 |
| | Hypertension | 1 |
| | Age \geq 65 years | 1 |
| | Age \geq 75 years | 1 |
| | Diabetes mellitus | 1 |
| | Stroke (ischemic stroke, transient ischemic disease, or systemic embolism) | 2 |
| | Vascular disease (myocardial infarction, peripheral arterial disease, or aortic plaque) | 1 |
| | Female | 1 |
| HAS-BLED (10) | Hypertension | 1 |
| | Abnormal renal function | 1 |
| | Abnormal hepatic function | 1 |
| | Stroke (ischemic stroke or transient ischemic attack) | 1 |
| | Bleeding | 1 |
| | Labile international normalized ratio* | 1 |
| | Elderly Age (\geq 65 years) | 1 |
| | Drugs (aspirin, clopidogrel, or non-steroidal anti-inflammatory drugs) | 1 |
| | Alcohol intake | 1 |

*Not included due to unavailable information

Table 8

Definition of concomitant medication

| Drug | Definition | |
|------------------------------------|-----------------------------------|---|
| | ATC code | Generic name |
| Aspirin | - | Aspirin, aspirin dihydroxyaluminum aminoacetate magnesium carbonate |
| Ticlodipine | - | Ticlopidine hydrochloride |
| Cilostazole | - | Cilostazole |
| Clopidogrel | - | Clopidogrel sulfate |
| ARB or ACE | C09A0, C09C0, C09D1 | - |
| Beta blocker | C07A0 | - |
| Amiodarone | - | Amiodarone hydrochloride |
| Procainamide | - | Procainamide hydrochloride |
| Disopyramide | - | Disopyramide, disopyramide phosphate |
| Flecainide | - | Flecainide hydrochloride |
| Pilsicainide | - | Pilsicainide hydrochloride |
| CCB | C08A0 | - |
| Digoxin | - | Digoxin, metildigoxin |
| Diuretics | C03A1, C03A2, C03A3, C03A7, C03A9 | - |
| Statins | C10A1 | - |
| Proton pump inhibitor | A02B2 | - |
| H ₂ receptor antagonist | A02B1 | - |

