9.7 DATA ANALYSIS

9.7.1 Main analysis

Propensity Score Matching

[figure not shown]
To reduce channelling bias, dabigatran and warfarin study groups will be established using PS matching method, on a 1:1 fixed ratio. The nearest neighbour method of propensity score matching within a caliper of 0.10 of the standard deviation of the estimated logit will be used to select the matched samples. All pre-defined variables has been evaluated in CTMS 1160.279 for inclusion into the model. Covariates with less than 10 patients present in the data was eliminated as well as CHADs which showed high co-linearity with CHADsVASC which was eliminated from the model. Otherwise, all pre-defined variables will be used. For further detail of the methodology of PS matching, please see the study protocol CTMS 1160.279.

For the primary outcome

Incidence rates of each treatment cohort (warfarin and dabigatran) will be provided, and all analysis will be conducted on the PS matched sample. The hazard ratio (HR) of stroke/systemic embolism for the dabigatran cohort as compared to the warfarin cohort and its 95% confidence interval (CI) will be estimated from the PS matched cohort using a Cox regression model with treatment group as the dependent variable. No additional covariates are considered in the Cox model as no residual imbalance was identified after PS matching (1160.276 study report, c15432368)." There will be no formal hypothesis testing. Kaplan Meier analysis with the number of patients at risk during the follow-up period after the index date and the number of events for ischemic stroke and major bleeding will be provided.

For the secondary outcome

Same analysis method will be utilized to calculate HR for the outcome of major bleeding.

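### NSAID use, most alcohol codes, the Table 6 renal item and part of its hepatic and bleeding items reach the propensity score only inside the HAS-BLED total, so the match balances their sum and not each item.

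*Combined protocol and SAP*

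**What the plan says.** Section 9.3.3 states: "Logistic regression model was used to estimate propensity scores based on all covariates listed below". The list contains "HAS-BLED Score" as one covariate. It also has separate terms for age, hypertension, stroke/TIA, liver disease, bleeding, peptic ulcer, kidney impairment, aspirin and clopidogrel. It has none for NSAIDs or alcohol, and NSAIDs are absent from the concomitant-medication definitions in Table 8.

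NSAIDs are defined in Table 6 ("Non-steroidal anti-inflammatory drugs defined by ATC code (EPHMRA) as M01A") to feed one shared point in Table 7: "Drugs (aspirin, clopidogrel, or non-steroidal anti-inflammatory drugs) | 1". Alcohol is also defined only in Table 6: "F10, G312, G621, G721, I426, K292, K70, K860, L278, O354, T51, Z714, Z721". The HAS-BLED renal item is "I12, I13, N00-N05, N07, N11, N14, N17-N19, Q61", whereas the separate renal covariate in Table 4 is "Kidney impairment | N28".

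Section 9.7.1 drops covariates present in fewer than 10 patients, and CHADS2 for collinearity. It then says: "Otherwise, all pre-defined variables will be used". Matching is 1:1 nearest neighbour on the logit, with a caliper of 0.10 SD. The Cox model contains treatment only, on the ground that an earlier study found no residual imbalance after matching.

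**The concern.** A total gives its components one common coefficient. For components with no term of their own, the model can equalise the sum but not the parts. If one such component drives the choice between dabigatran and warfarin, the matched groups keep some of that difference, and the other components become unequal in the opposite direction to make the sum agree. This can happen to a factor, such as NSAID use, that was equal before matching.

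By the plan's own use of HAS-BLED these are bleeding-risk factors, and major bleeding is the secondary outcome. A balanced mean HAS-BLED would not reveal the problem, and an unadjusted Cox model would not correct it. The plan does not say that balance was checked, or will be checked, on the individual items.

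**Working it through.** **Step 1: which items lack a term of their own.** Each HAS-BLED item in Tables 6 and 7 was set against the 9.3.3 list and Tables 4 and 8.

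| HAS-BLED item | Covered by another term | Not covered |
|---|---|---|
| Hypertension, age, stroke/TIA | Yes | None |
| Drugs | Aspirin, clopidogrel | NSAIDs (M01A) |
| Alcohol | K70 (liver), K292 (bleeding) | The other 11 of 13 codes |
| Renal | No code shared with N28; I12 and I13 lie in the hypertension range I10-I15, which does not isolate renal disease | All N codes and Q61 |
| Hepatic | K704, K72, K766 (liver K70-K77) | B150, B160, B162, B190, I85 |
| Bleeding | I60-I62 (stroke); K250, K260, K270, K280, K290 (bleeding K25-K29) | D62, J942, H113, H356, H431, N02, N95, R04, R31, R58, S063-S066 |

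Several uncovered bleeding codes (D62, H113, H356, H431, R04, R31, R58) are also codes of the secondary outcome in 9.3.2.2.

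**Step 2: does balancing the sum unbalance the parts?** The documents give no prevalences or odds ratios, so all inputs here are assumptions: renal item about 10%, with odds ratio 0.5 / 0.35 / 0.2 for receiving dabigatran; NSAIDs 25%, unrelated to drug choice; alcohol about 2%; bleeding item about 9%. Matching was simulated as 1:1 nearest neighbour with a caliper of 0.10 SD of the logit. The table shows dabigatran v warfarin after matching with the total in the model. The renal and NSAID rows come from one simulation; the alcohol and bleeding rows come from another with similar inputs.

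| Item | OR 0.5 | OR 0.35 | OR 0.2 |
|---|---|---|---|
| Renal | 6.4% v 10.8% | 4.8% v 10.5% | 2.9% v 10.5% |
| NSAID | 25% v 23.0% | 25% v 22.4% | 25% v 21.4% |
| Alcohol | 2.1% v 1.7% | 2.1% v 1.6% | 2.1% v 1.5% |
| Bleeding | 9.3% v 8.4% | 9.3% v 8.2% | 9.3% v 7.7% |

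Mean HAS-BLED still agreed (for example 2.207 v 2.205). The standardised difference is (p1 - p2) / sqrt[(p1(1-p1) + p2(1-p2))/2]:
- Renal at OR 0.5: (0.064 - 0.108) / 0.280 = -0.16. At OR 0.2: -0.31.
- NSAID: 0.05 to 0.09.

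A further simulation used 16,000 patients, a reduced model and a wider set of assumptions (renal 10-15%, odds ratio 0.3-0.7, NSAIDs 20-30%). The NSAID standardised difference moved from about 0 to between 0.027 and 0.105. In its strongest settings renal imbalance fell only from -0.305 to -0.241 and from -0.370 to -0.265. With the renal odds ratio at 1.0 the NSAID difference was 0.001, so no harm. With separate terms added, all four items were within about 0.006.

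**Step 3: effect on the bleeding hazard ratio.** For one item with risk ratio RR, the bias factor is [1 + p_dabigatran(RR - 1)] / [1 + p_warfarin(RR - 1)]. At OR 0.5 and RR 1.5:
- Renal: 1.032 / 1.054 = 0.979
- NSAID: 1.125 / 1.115 = 1.009
- Alcohol: 1.0105 / 1.0085 = 1.002
- Bleeding: 1.0465 / 1.042 = 1.004

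The product, treating the items as independent, is 0.994. In the same way:

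| Same RR for all items | OR 0.5 | OR 0.35 | OR 0.2 |
|---|---|---|---|
| RR 1.5, net | 0.994 | 0.992 | 0.990 |
| RR 2, net | 0.988 | 0.983 | 0.979 |
| RR 2, renal part only | 0.960 | 0.948 | 0.931 |
| RR 2, other three only | 1.029 | 1.037 | 1.051 |

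With equal risks the net shift is about 0.5-2% downward. The last two rows show that the sign depends on how renal risk compares with the risk carried by the other items.

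**The case against.** The strongest counter-case has five parts.

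**The total helps more than it harms.** A reader might infer that matching on these covariates introduces confounding and pushes the bleeding hazard ratio up, by about 1-3% from the NSAID gap alone. That counts one side only: the excess of NSAIDs, alcohol and bleeding in the dabigatran group mirrors a larger renal excess left in the warfarin group. In a simulation with a reduced model and equal risk ratios, the net factor with the total was 0.997 / 0.996 / 0.994 at RR 1.5 and 0.993 / 0.991 / 0.987 at RR 2. Leaving HAS-BLED out gave 0.975 / 0.965 / 0.953 and 0.953 / 0.933 / 0.912. In that scenario the total removes most of the confounding. This stands.

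**Many items do have terms.** It would be wrong to say that every Table 6 item enters only through the total, or that patients are matched on the total itself. Matching is on the propensity score, and Step 1 shows what is covered. This stands.

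**The shift is small against the precision.** Follow-up is about 2 x 4,427 x 0.40487 = 3,585 patient-years. At an assumed bleeding rate of 2-10% a year there are about 72-358 events. The 95% limits are then a factor exp(1.96 x 2/sqrt(events)) = 1.59 to 1.23 either side of the estimate, and the analysis is declared exploratory. This stands for the net shift. The renal gap itself, at 0.16 to 0.31, exceeds the customary 0.1.

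**A balance table might show it.** The abstract promises patient characteristics before and after matching and does not limit them to model covariates, and the matching detail is in a protocol that is not supplied. So it cannot be said that the imbalance would go unseen. But nothing in this plan requires these items to be shown.

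**No evidence that it happened.** This is true: channelling on these items is assumed throughout. The plan does, however, name channelling as the bias that matching is meant to address, and it lists kidney impairment as a covariate.

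**Conclusion.** The point holds in a limited form. NSAID use, most alcohol codes, the Table 6 renal item, and the hepatic and bleeding codes outside Table 4 have no propensity-score term of their own. The model balances their sum only. If one of them is channelled, part of its imbalance remains and the others are displaced in the opposite direction. Under the assumed inputs the remaining renal gap is about 6% v 11% to 3% v 10%, and the induced NSAID gap is 25% v 23% to 21%. The net effect on the major-bleeding hazard ratio is about 0.5-2% if the items carry equal risk, and it can go either way if they do not. It is nil if none is channelled.

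The documents do not support reading this as evidence that the match has created confounding, that the bleeding hazard ratio is biased against dabigatran, or that imbalance has occurred. This is a worthwhile improvement to the specification, not a flaw that invalidates the comparison.

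**What to change.** In 9.3.3, add yes/no covariates for baseline NSAID use (M01A) and alcohol intake (Table 6 codes), and enter the Table 6 renal, hepatic and bleeding items as their own yes/no terms. Use them in place of the HAS-BLED total or alongside it, checking collinearity if both are kept. Re-run the match and report before/after balance for every item. If the match is not redrawn, reporting post-match balance on each item is the minimum.

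The cost is about five more model terms from codes the plan already defines, one re-run and a longer balance table. In simulation the number of matched pairs did not change (for example 4,222 v 4,222). Any item present in fewer than 10 patients would drop out under the plan's existing rule.

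### Table 8 counts the ARB+diuretic code C09D1 as ARB/ACE use but omits the ARB+CCB code C09D3 from both the ARB/ACE and CCB rows, so patients whose only such claims are C09D3 are coded no on two propensity-score covariates

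*Combined protocol and SAP*

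**What the plan says.** Section 9.3.3 introduces the covariate list with "Logistic regression model was used to estimate propensity scores based on all covariates listed below". Among the yes/no drug covariates, headed "Concomitant medication (prescription claims within the baseline period", it names "angiotensin receptor blockers or angiotensin converting enzyme inhibitors", "calcium-channel blocker" and diuretics. Section 9.2 sets the baseline period at 12 months up to and including the index date.

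Table 8 turns these covariates into codes. The first is "ARB or ACE | C09A0, C09C0, C09D1". The CCB row holds only C08A0. The diuretics row reads "Diuretics | C03A1, C03A2, C03A3, C03A7, C03A9". The generic-name column is a dash for all three, so the ATC codes are the only route to a yes.

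Table 5, which lists anti-hypertensive drugs, has a separate row for combination agents: "C09D1 (ARB and diuretics), C09D3 (ARB and CCB". It feeds the hypertension definition in Table 4, whose prescription part reads "Prescribed 2 or more types of anti-hypertensive (defined in Table 2b". The cross-reference is to a Table 2b, but the class list is in Table 5.

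Section 9.7.1 makes 1:1 matching on the propensity score the only confounding adjustment. The Cox model has no further covariates, because an earlier study report found no residual imbalance after matching.

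**The concern.** Table 8 treats two sibling codes differently and gives no reason. Both contain an ARB. One counts as ARB/ACE use and the other does not, and the second also contains a CCB that the CCB row misses. No single rule produces this. If only single-agent products counted, C09D1 would not be in the ARB/ACE row. If a combination counted towards each of its components, C09D3 would be in two rows.

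At stake is the accuracy of two matching covariates for the same identifiable patients. Matching would pair someone taking an ARB and a CCB as if they took neither. A balance check on the same coding could not show this, because the groups can look balanced on the miscoded variables. The planned description of patient characteristics before and after matching would also understate use of both classes, whether or not the hazard ratio moves.

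**Working it through.** The plan states no figure on this point, so there is none to reproduce. The check compares code lists and then sizes the problem under a stated assumption.

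1. Inputs from Table 8: ARB/ACE = {C09A0, C09C0, C09D1}; CCB = {C08A0}; diuretics = {C03A1, C03A2, C03A3, C03A7, C03A9}. Input from Table 5: C09D1 is ARB plus diuretic; C09D3 is ARB plus CCB.

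2. Each combination code was matched against all ATC codes in Table 8, by code and by prefix. C09D1 matches the ARB/ACE row only. C09D3 matches no row.

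3. Consequence for a patient with a C09D3 claim in the baseline period, who takes both classes:

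| Other claims in baseline | ARB/ACE coded | CCB coded | Covariates wrong |
|---|---|---|---|
| None of C09A0, C09C0, C09D1, C08A0 | no | no | 2 |
| C08A0 only | no | yes | 1 |
| C09A0, C09C0 or C09D1, but not C08A0 | yes | no | 1 |
| C08A0 and at least one of C09A0, C09C0, C09D1 | yes | yes | 0 |

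Only the first row loses both covariates.

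4. Size. The documents do not say how many patients fall in that first row. Take an assumed proportion p and the 4,421 per group of Table 9 (section 9.5):

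- p = 1%: 0.01 × 4,421 = 44.2, about 44 per arm
- p = 5%: 0.05 × 4,421 = 221.05, about 221 per arm
- p = 10%: 0.10 × 4,421 = 442.1, about 442 per arm

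The text of section 9.5 gives 4,427 instead of 4,421. With that number the results are 44.3, 221.4 and 442.7, which is no material change.

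5. Effect on the hazard ratio. This cannot be computed: it needs the C09D3 prevalence in each arm and its relation to outcome given the other covariates, and the documents give neither.

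6. Secondary check: a patient whose only diuretic is in a C09D1 product is coded yes for ARB/ACE and no for diuretics.

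**The case against.** The strongest reply is that the omission matters little. These are two of about 40 listed covariates. Related information stays in the model: hypertension history is a covariate, its Table 5 drug list does include C09D3, and hypertension also enters CHA2DS2-VASc and HAS-BLED. Miscoding in the same proportion in both arms leaves little differential imbalance, and nothing in the documents suggests that C09D3 use differs between warfarin and dabigatran starters. The study is declared exploratory, without formal testing. This stands as an argument about size. It does not repair the coding: the hypertension variable does not set the ARB/ACE or CCB covariates, and the baseline table would be wrong in any case.

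A second reply is that Tables 5 and 8 serve different purposes, no text requires them to agree, and Table 5 itself keeps combinations apart from the single classes. That is fair, but the inconsistency lies within Table 8, which accepts one ARB combination and leaves out the other. The reply has more force for diuretics: Table 5's own diuretics row has the same five codes as Table 8 and also leaves out C09D1. That part is therefore only a suggestion.

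A reader might infer more than the documents support:

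- That every combination tablet is lost. It is not: C09D1 counts as ARB/ACE use.
- That every ARB+CCB user is coded no twice. One separate claim in the 12 months sets that class to yes.
- That anticoagulant exposure is misclassified. Only covariates are affected.
- That the hazard ratio is biased by a known amount. No figure in the documents allows that statement.

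**Conclusion.** The point holds in a narrow form. As Table 8 is written, C09D3 sets neither the ARB/ACE nor the CCB covariate, although Table 5 identifies it as containing both classes and its sibling C09D1 is counted as ARB/ACE. Patients with no other qualifying claim in the baseline period are wrong on both covariates, and some others are wrong on one.

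The range of about 44 to 442 patients per arm rests entirely on the assumed 1% to 10% and is illustrative. The effect on the hazard ratio is probably small: bias would need C09D3 use to differ between arms and to relate to outcome beyond what the remaining covariates capture. This is a minor correction. It is worth making because the code list is wrong on its face and the missing code already stands in the protocol.

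**What to change.** Add C09D3 to both the ARB/ACE row and the CCB row of Table 8, or, if the omission is deliberate, state why. A sentence saying that a combination product counts towards each of its components would settle the rule. Under that rule, consider adding C09D1 to the diuretics row for consistency.

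Then re-run the propensity model, the matching and the balance check, and confirm that the statement in section 9.7.1 on residual imbalance still holds with the corrected coding.

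The edits themselves are two code insertions, or three with the diuretics row. The real cost is the re-run: section 9.7.1 says that the covariates were already evaluated in study 1160.279, so scores and matched pairs may shift and the matched sample may change slightly. Outcomes, the target of estimation and the main analysis method stay as they are.
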